- Collect a blood sample of approximately 5 mL for immunogenicity prior to vaccination (a topical anesthetic is permitted).
- Administer a single 0.5-mL injection of c7vPnC into the left anterolateral thigh.

- Site staff will observe the subject for at least 30 minutes after vaccination for any acute reactions. Record any AEs on the CRF and on an SAE form as applicable. Record concomitant medications used to treat SAEs and NDCMCs.
- Issue the subject's legally acceptable representative an e-diary (if device needed). Provide and review instructions on use and completion of the e-diary. Ask the subject's legally acceptable representative to complete the e-diary from Day 1 to Day 7, with Day 1 being the day of vaccination. Provide thermometer or measuring device if needed.

- Ask the subject's legally acceptable representative to contact the investigator site staff or investigator immediately during the 7-day postvaccination period if the subject experiences fever >104.0°F (>40.0°C), redness or swelling at the injection site measuring >14 measuring device units (>7 cm), or severe injection site pain (causes limitation of limb movement) to determine if the event requires further assessment by the investigator.
- Remind the subject's legally acceptable representative to contact the investigator or investigator site staff as soon as possible if any significant illness or medical event (eg, emergency room visit or hospitalization) occurs.
- Remind the subject's legally acceptable representative that use of prophylactic antipyretic/pain medication, while permitted, is not recommended on the day of investigational product administration (before or after vaccination).
- The investigator or an authorized designee completes the CRF and updates the investigational product accountability records.

6.2.10. Group 2 Visit 10 (Follow-up: 14-Month Visit, 28 to 42 Days After Dose 4)

- Ensure and document that the subject continues to be eligible for the study (see Section 6.5 for withdrawal information), and none of the temporary delay criteria are met.
- Record vaccines administered since Visit 9 as described in Section 5.7.4.
- Review the subject's e-diary data with the subject's legally acceptable representative; collect stop dates of any e-diary events ongoing on the last day that the e-diary was completed and record stop dates in the CRF.
- Collect the e-diary (if device provided).
- Determine whether any AEs (includes nonserious AEs, SAEs, or NDCMCs) have occurred since the previous visit and follow up on any previously reported events to determine the outcome (ie, record stop dates or confirm if they are still continuing) and record as described in Section 8, and record concomitant medications used to treat SAEs and NDCMCs.
- Collect a blood sample of approximately 5 mL for immunogenicity assessments (a topical anesthetic is permitted).
- Remind the subject's legally acceptable representative to contact the investigator or investigator site staff immediately if any significant illness or medical event (eg, emergency room visit or hospitalization) occurs.
- The investigator or an authorized designee completes the CRF.

6.2.11. Group 2 Visit 11 (Follow-up: 19-Month Phone Contact, 168 to 196 Days After Dose 4)

- Contact the subject's legally acceptable representative by telephone approximately 6 months after the last dose of c7vPnC; this contact should be attempted for all subjects who have received at least 1 dose of c7vPnC, unless the subject's legally acceptable representative has withdrawn consent.
- Determine whether any SAEs or NDCMCs have occurred since the previous visit and follow up on any previously reported events to determine the outcome (ie, record stop dates or confirm if they are still continuing) and record as described in Section 8, and record concomitant medications used to treat SAEs and NDCMCs.
- The investigator or an authorized designee completes the CRF.

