3. STUDY DESIGN

This will be a Phase 2, multicenter, randomized, active-controlled, open-label study with a 3-arm parallel design, conducted at investigator sites in the United States. A total of 565 infants \ge 42 to \le 98 days of age at the time of consent will be enrolled and randomized in a 1:1:1 ratio to receive a vaccine series with:

- c7vPnC coadministered with Prevnar 13 (Group 1 coadministration);
- c7vPnC given 1 month after Prevnar 13 (Group 2 staggered administration); or
- Prevnar 13 alone as the active control group (Group 3 control with Supplemental Dose).
 A single dose of c7vPnC will be administered after the Prevnar 13 series is completed in this group.

In all groups, Prevnar 13 will be administered at 2, 4, 6, and 12 months of age. c7vPnC will be administered at 2, 4, 6, and 12 months of age in Group 1; at 3, 5, 7, and 13 months of age in Group 2; and at 13 months of age in Group 3. **Note:** In this document, and related study documents, vaccine (investigational product) Doses 1, 2, 3, and 4 specifically refer to the doses of c7vPnC administered in Groups 1 and 2, or the doses of Prevnar 13 administered in the control group (Group 3). The dose of c7vPnC administered in Group 3 will be referred to as the Supplemental Dose. See Table 1 for a summary of study groups and key procedures.

Table 1. Summary of Study Groups and Key Procedures

·	2 mo/o	3 mo/o	4 mo/o	5 mo/o	6 mo/o	7 mo/o	8 mo/o	12 mo/o	13 mo/o	14 mo/o	18 mo/o	19 mo/o
Group 1 Coadmin. c7vPnC (n= ~188)	c7vPnC Dose 1 Prev13		c7vPnC Dose 2 Prev13		c7vPnC Dose 3 Prev13	Blood draw		Blood draw c7vPnC Dose 4 Prev13	Blood draw		Phone contact	
Group 2 Staggered c7vPnC (n= ~188)	Prev13	c7vPnC Dose 1	Prev13	c7vPnC Dose 2	Prev13	Blood draw c7vPnC Dose 3	Blood draw	Prev13	Blood draw c7vPnC Dose 4	Blood draw		Phone contact
Group 3 Control (n= ~188)	Prev13 Dose 1		Prev13 Dose 2		Prev13 Dose 3	Blood draw		Blood draw Prev13 Dose 4	Blood draw c7vPnC Suppl. Dose	CCI		Phone contact

Abbreviations: Coadmin. = coadministered; mo/o = months old; Prev13 = Prevnar 13; Suppl. = supplemental.

Vaccine containing diphtheria, tetanus, and acellular pertussis antigens will be administered at 2, 4, and 6 months of age. This is as part of routine standard of care in the United States,

Other routine pediatric vaccines may be administered in this study, with or without certain restrictions.

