5.4. Administration

Investigational product, ie, c7vPnC for Groups 1 and 2 and the Supplemental Dose (Group 3), and Prevnar 13 (control) in Group 3, will be administered into the thigh of the left leg as specified below.

- Group 1: Each dose (0.5 mL) of c7vPnC will be administered intramuscularly (IM) into the anterolateral thigh muscle of the left leg and each dose (0.5 mL) of Prevnar 13 will be administered IM into the anterolateral thigh muscle of the right leg.
- Group 2: Each dose (0.5 mL) of Prevnar 13 (given 1 month before the c7vPnC dose) will be administered IM into the anterolateral thigh muscle of the right leg and each dose (0.5 mL) of c7vPnC will be administered IM into the anterolateral thigh muscle of the left leg.
- Group 3: Prevnar 13 (0.5 mL) and the Supplemental Dose of c7vPnC will be administered IM into the anterolateral thigh muscle of the left leg.

Other permitted routine pediatric injectable vaccines (including diphtheria, tetanus, and acellular pertussis [DTaP]-containing vaccines) must be administered in a different limb from the site of administration of c7vPnC in Groups 1 and 2 or Prevnar 13/c7vPnC Supplemental Dose in Group 3. Concomitant injectable vaccines will be administered with Prevnar 13 (not c7vPnC) in Group 2. The location of the injection of each vaccine administered (investigational product and other) will be recorded.

Standard vaccination practices must be observed and vaccine must not be injected into blood vessels. Appropriate medication and other supportive measures for management of an acute hypersensitivity reaction should be available in accordance with local guidelines for standard immunization practices.

Administration of vaccines in this study should be performed by an appropriately qualified, Good Clinical Practice (GCP)-trained, and vaccine-experienced member of the study staff (eg, physician, nurse, physician's assistant, nurse practitioner, pharmacist, or medical assistant) as allowed by local, state, and institutional guidance.

Vaccine administration details will be recorded on the case report form (CRF).

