- Issue the subject's legally acceptable representative an e-diary (if device needed). Provide and review instructions on use and completion of the e-diary. Ask the subject's legally acceptable representative to complete the e-diary from Day 1 to Day 7, with Day 1 being the day of vaccination. Provide thermometer or measuring device if needed.
- Ask the subject's legally acceptable representative to contact the investigator site staff or investigator immediately during the 7-day postvaccination period if the subject experiences fever >104.0°F (>40.0°C), redness or swelling at the injection site measuring >14 measuring device units (>7 cm), or severe injection site pain (causes limitation of limb movement) to determine if the event requires further assessment by the investigator.
- Remind the subject's legally acceptable representative to contact the investigator or investigator site staff as soon as possible if any significant illness or medical event (eg, emergency room visit or hospitalization) occurs.
- Remind the subject's legally acceptable representative that use of prophylactic antipyretic/pain medication, while permitted, is not recommended on the day of investigational product administration (before or after vaccination).
- The investigator or an authorized designee completes the CRF and updates the investigational product accountability records.

6.1.6. Group 1 Visit 6 (Follow-up: 13-Month Visit, 28 to 42 Days After Dose 4)

- Ensure and document that the subject continues to be eligible for the study (see Section 6.5 for withdrawal information), and none of the temporary delay criteria are met.
- Record vaccines administered since Visit 5 as described in Section 5.7.4.
- Review the subject's e-diary data with the subject's legally acceptable representative; collect stop dates of any e-diary events ongoing on the last day that the e-diary was completed and record stop dates in the CRF.
- Collect the e-diary (if device provided).
- Determine whether any AEs (includes nonserious AEs, SAEs, or NDCMCs) have occurred since the previous visit and follow up on any previously reported events to determine the outcome (ie, record stop dates or confirm if they are still continuing) and record as described in Section 8, and record concomitant medications used to treat SAEs and NDCMCs.

- Collect a blood sample of approximately 5 mL for immunogenicity assessments (a topical anesthetic is permitted).

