- Determine whether any AEs (includes nonserious AEs, SAEs, and NDCMCs) have occurred since the previous visit and follow up on any previously reported events to determine the outcome (ie, record stop dates or confirm if they are still continuing) and record as described in Section 8, and record concomitant medications used to treat SAEs and NDCMCs.
- Measure and record the subject's rectal temperature (${}^{\circ}F/{}^{\circ}C$).
- Administer a single 0.5-mL injection of c7vPnC into the left anterolateral thigh.

After vaccination:

• Site staff will observe the subject for at least 30 minutes after vaccination for any acute reactions. Record any AEs on the CRF and on an SAE form as applicable. Record concomitant medications used to treat SAEs and NDCMCs.

- Issue the subject's legally acceptable representative a measuring device to measure injection site reactions and a digital thermometer and provide instructions on their use.
- Issue the subject's legally acceptable representative an e-diary (device or application). Provide instructions on use and completion of the e-diary. Ask the subject's legally acceptable representative to complete the e-diary from Day 1 to Day 7, with Day 1 being the day of vaccination.
- Ask the subject's legally acceptable representative to contact the investigator site staff or investigator as soon as possible during the 7-day postvaccination period if the subject has a fever >104.0°F (>40.0°C), redness and/or swelling at the injection site measuring >14 measuring device units (>7 cm), or severe injection site pain (causes limitation of limb movement) to determine if the event requires further assessment by the investigator.
- Ask the subject's legally acceptable representative to contact the investigator or investigator site staff as soon as possible if any significant illness or medical event (eg, emergency room visit or hospitalization) occurs during the study period.
- Remind the subject's legally acceptable representative that use of prophylactic antipyretic/pain medication, while permitted, is not recommended on the day of investigational product administration (before or after vaccination).
- The investigator or an authorized designee completes the CRF and updates the investigational product accountability records.

6.2.3. Group 2 Visit 3 (Prevnar 13: 4-Month Visit, 42 to 63 Days After Prevnar 13 at Visit 1)

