- Administer a single 0.5-mL injection of Prevnar 13 into the right anterolateral thigh.
- Administer DTaP-containing vaccine and other permitted vaccines (to be administered into a limb other than the left leg).

- Remind the subject's legally acceptable representative to contact the investigator or investigator site staff as soon as possible if any significant illness or medical event (eg, emergency room visit or hospitalization) occurs during the study period.
- Remind the subject's legally acceptable representative that use of prophylactic antipyretic/pain medication, while permitted, is not recommended on the day of investigational product administration (before or after vaccination).
- The investigator or an authorized designee completes the CRF and updates the investigational product accountability records.

6.2.6. Group 2 Visit 6 (c7vPnC Dose 3: 7-Month Visit, 21 to 35 Days After Prevnar 13 at Visit 5)

- Ensure and document that the subject continues to be eligible for the study (see Section 6.5 for withdrawal information), and none of the temporary delay criteria are met.
- Record vaccines administered since Visit 5 as described in Section 5.7.4.
- Determine whether any AEs (includes nonserious AEs, SAEs, and NDCMCs) have
 occurred since the previous visit and follow up on any previously reported events to
 determine the outcome (ie, record stop dates or confirm if they are still continuing) and
 record as described in Section 8, and record concomitant medications used to treat SAEs
 and NDCMCs.
- Measure and record the subject's rectal temperature (${}^{\circ}F/{}^{\circ}C$).
- Collect a blood sample of approximately 5 mL for immunogenicity prior to vaccination (a topical anesthetic is permitted).
- Administer a single 0.5-mL injection of c7vPnC into the left anterolateral thigh.

- Site staff will observe the subject for at least 30 minutes after vaccination for any acute reactions. Record any AEs on the CRF and on an SAE form as applicable. Record concomitant medications used to treat SAEs and NDCMCs.
- Confirm that the e-diary is working and review instructions if necessary. Remind the subject's legally acceptable representative to complete the e-diary from Day 1 to Day 7, with Day 1 being the day of vaccination. Provide thermometer or measuring device if needed.

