- Remind the subject's legally acceptable representative that use of prophylactic antipyretic/pain medication, while permitted, is not recommended on the day of investigational product administration (before or after vaccination).
- The investigator or an authorized designee completes the CRF.

6.2.8. Group 2 Visit 8 (Prevnar 13: 12-Month Visit, 365 to 386 Days of Age)

- Ensure and document that the subject continues to be eligible for the study (see Section 6.5 for withdrawal information).
- Record vaccines administered since Visit 7 as described in Section 5.7.4.
- Determine whether any SAEs or NDCMCs have occurred since the previous visit and follow up on any previously reported events to determine the outcome (ie, record stop dates or confirm if they are still continuing) and record as described in Section 8, and record concomitant medications used to treat SAEs and NDCMCs.
- Administer a single 0.5-mL injection of Prevnar 13 into the right anterolateral thigh.

• Administer permitted vaccines (to be administered into a limb other than the left leg).

After vaccination:

- Remind the subject's legally acceptable representative to contact the investigator or
 investigator site staff as soon as possible if any significant illness or medical event
 (eg, emergency room visit or hospitalization) occurs.
- Remind the subject's legally acceptable representative that use of prophylactic antipyretic/pain medication, while permitted, is not recommended on the day of investigational product administration (before or after vaccination).
- The investigator or an authorized designee completes the CRF and updates the investigational product accountability records.

6.2.9. Group 2 Visit 9 (c7vPnC Dose 4: 13-Month Visit, 21 to 35 Days After Prevnar 13 at Visit 8)

- Ensure and document that the subject continues to be eligible for the study (see Section 6.5 for withdrawal information), and none of the temporary delay criteria are met.
- Record vaccines administered since Visit 8 as described in Section 5.7.4.
- Determine whether any SAEs or NDCMCs have occurred since the previous visit and follow up on any previously reported events to determine the outcome (ie, record stop dates or confirm if they are still continuing) and record as described in Section 8, and record concomitant medications used to treat SAEs and NDCMCs.
- Measure and record the subject's rectal temperature (°F/°C).

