8.1.4. Time Period for Collecting AE/SAE/NDCMC Information

The time period for actively eliciting and collecting AEs, SAEs, and NDCMCs ("active collection period") for each subject begins from the time the subject's legally acceptable representative provides informed consent, which is obtained before the subject's participation in the study (ie, before undergoing any study-related procedure and/or receiving

investigational product). AEs will be collected through 1 month after Dose 3 and from Dose 4 through 1 month after Dose 4 or 1 month after the Supplemental Dose in Group 3. NDCMCs and SAEs will be collected from signing of informed consent through 6 months after Dose 4 or the Supplemental Dose. An NDCMC is defined as a disease or medical condition, not previously identified, that is expected to be persistent or is otherwise long-lasting in its effects.

For subjects who are screen failures, the active collection period ends when screen failure status is determined.

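### Group 2 nonserious AEs are not collected in the 21 to 35 days between the 12-month Prevnar 13 dose and c7vPnC Dose 4; asking about them at Visit 9 would be a cheap improvement, not the correction of an error

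*Protocol*

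**What the plan says.** Protocol section 3 fixes the dose numbering: "vaccine (investigational product) Doses 1, 2, 3, and 4 specifically refer to the doses of c7vPnC administered in Groups 1 and 2". In Group 2, Dose 4 is therefore the 13-month c7vPnC dose at Visit 9. The 12-month Prevnar 13 dose at Visit 8 carries no dose number.

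Section 8.1.4 sets the collection periods: "AEs will be collected through 1 month after Dose 3 and from Dose 4 through 1 month after Dose 4". Footnote a to the table in 8.1 gives the same limits for nonserious AEs. SAEs and NDCMCs are collected throughout.

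At Group 2 Visit 9 (6.2.9) the event question is to "Determine whether any SAEs or NDCMCs have occurred since the previous visit". A separate bullet at that visit says "Ensure and document that the subject continues to be eligible for the study". Visit 10 (6.2.10) asks about all AEs, but looks back only to Visit 9.

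Elsewhere the question after a Prevnar 13 dose is wider. Group 2 Visits 2 and 4 (6.2.2, 6.2.4) say "Determine whether any AEs (includes nonserious AEs, SAEs, and NDCMCs) have occurred since the previous visit", and Visit 6 (6.2.6) asks the same. After the 12-month dose, Group 1 (6.1.6) and Group 3 (6.3.6) say "Determine whether any AEs (includes nonserious AEs, SAEs, or NDCMCs) have occurred since the previous visit".

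Section 5.4 adds: "Concomitant injectable vaccines will be administered with Prevnar 13 (not c7vPnC) in Group 2". SAP 6.1.3.1 reports AE proportions for each group, with the Dose 4 and Supplemental Dose intervals shown separately.

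**The concern.** The Protocol Summary gives the study's purpose as describing c7vPnC both coadministered with Prevnar 13 and given a month after it, and section 1.2.2.3 says the data are to inform Phase 3 design. The staggered booster takes two vaccination visits. Unsolicited nonserious AEs are collected after only one of them.

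The Dose 4 row for Group 1 takes in c7vPnC, Prevnar 13 and anything given alongside, such as MMR. The Group 2 row takes in the c7vPnC visit but not the Prevnar 13 visit, where the concomitant injectables are given. A reader wanting the unsolicited booster experience of the staggered schedule cannot assemble it, and data never collected cannot be recovered.

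A second, smaller point concerns the decision to give Dose 4. The eligibility check reaches, through 6.5, exclusion criterion 7 (a previous severe reaction to a vaccine). Section 8.3 notes that a severe event need not be serious. After Visit 8 there is no scheduled 30-minute observation and no e-diary, and the contact rule for severe reactions in 6.4 is tied to c7vPnC doses. A severe but nonserious reaction to the 12-month dose would come to light mainly if the family volunteered it. The two vaccines share a carrier protein and excipients, so the answer bears on Dose 4.

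**Working it through.** The plan states no figure for this interval, so the check sets the visit scripts side by side and then does simple arithmetic on the windows.

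| Prevnar 13 dose | Next visit | Days after that dose | Event question |
|---|---|---|---|
| Group 2, 2 months | Visit 2 (6.2.2) | 21 to 35 | all AEs |
| Group 2, 4 months | Visit 4 (6.2.4) | 21 to 35 | all AEs |
| Group 2, 6 months | Visit 6 (6.2.6) | 21 to 35 | all AEs |
| Group 2, 12 months | Visit 9 (6.2.9) | 21 to 35 | SAEs and NDCMCs only |
| Group 1, 12 months | Visit 6 (6.1.6) | 28 to 42 | all AEs |
| Group 3, 12 months | Visit 6 (6.3.6) | 28 to 42 | all AEs |

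**Pattern.** Three of Group 2's four Prevnar 13 doses are followed by an all-AE question. Group 3 has the same booster order (Prevnar 13 at 12 months, c7vPnC at 13 months) and is asked about all AEs before its c7vPnC dose. There is also a precedent for collecting outside the endpoint interval: Group 2 AEs between the 2-month Prevnar 13 dose and c7vPnC Dose 1 are collected from consent (8.1.4), although the endpoint starts at Dose 1 (2.1.2).

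**Coverage of the first 28 days after the 12-month Prevnar 13 dose.**
- Groups 1 and 3: follow-up comes at day 28 or later, so 28 of 28 days.
- Group 2: collected days = max(0, 28 − gap), where gap is the time from Visit 8 to Dose 4. Gap 21 gives 7; gap 28 gives 0; gap 35 gives 0. The range is 0 to 7 of 28 days.
- If MMR is given at Visit 8 (allowed by 5.7.3), the 28-day live-vaccine delay in 4.3.1 moves Dose 4 to about day 28 to 35, which gives 0 of 28.

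**Time not covered.** Protocol 3.3 assumes 15% dropout by Dose 3: 188 × 0.85 = 159.8, about 160 infants. Then 160 × 21 = 3,360 and 160 × 35 = 5,600 infant-days. If every infant had MMR at Visit 8 (an assumption), the lower end becomes 160 × 28 = 4,480. Further dropout before 12 months would reduce all of these.

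**Effect of the change.** Group 2 collection between Visit 8 and Dose 4 rises from 0 to 21 to 35 days. From Visit 8 to 1 month after Dose 4 it rises from 28 to 42 days to (21 + 28) to (35 + 42), that is 49 to 77 days. Group 1 has 28 to 42 days after its booster visit. Group 3 has 28 to 42 before the Supplemental Dose and 56 to 84 through 1 month after it.

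**The case against.** The strongest reply is that the rule is deliberate and consistent. The primary objective is the safety of c7vPnC. Group 2 doses are defined as c7vPnC doses, and the collection periods, the Visit 9 script, Protocol 9.4 and the SAP all follow. The Dose 4 interval is fully collected in every group. The 0 to 7 of 28 days arises only when the clock is started at Prevnar 13, which is not the plan's anchor in Group 2. No AE profile for the whole staggered regimen is listed as an endpoint, and nothing is tested. All of this stands, and it is why the point is an improvement and not a defect.

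The eligibility argument also needs trimming. A reader might infer that infants could be given Dose 4 after an unnoticed dangerous reaction. The documents do not support that. The SAE definition in 8.2.3 includes important medical events, with allergic bronchospasm treated in an emergency room or at home and convulsions without admission as examples, so the Visit 9 question already reaches them. Families are told at Visit 8 to report significant illness or medical events (6.2.8, also 6.4), section 8.1.2 provides for nonleading questioning, and eligibility is checked. What remains is a severe reaction that is neither serious nor medically important and that nobody volunteers.

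A reader might also take the Group 2 Dose 4 row to be c7vPnC alone. That is too absolute: 5.7.3 permits inactivated influenza vaccine in season and rotavirus vaccine at any time.

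Finally, the change would not make the two schedules fully comparable. Group 2 has no e-diary after any Prevnar 13 dose, and the collection windows would still differ in length.

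**Conclusion.** The gap is real and follows from the text: in Group 2, nonserious AEs with onset in the 21 to 35 days between Visit 8 and Dose 4 are not collected, although they are collected after the other three Prevnar 13 doses and after the same dose in Groups 1 and 3. The loss is limited to unsolicited nonserious AEs (other than NDCMCs) on the Prevnar 13 half of the staggered booster, plus an active question about such reactions before Dose 4.

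Two stronger conclusions are not supported. The primary AE endpoint counted from Dose 4 is neither incomplete nor biased in Group 2, because the interval it names is fully collected. Nor can a number of missed events be given: the 3,360 to 5,600 infant-days are exposure time, they rest on the Dose 3 dropout assumption carried forward to 12 months, and the documents contain no AE rate to apply to them.

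The change is worth making because it is cheap and because Group 3 already works this way.

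**What to change.** - In 6.2.9, replace the SAE/NDCMC question with the all-AE question used in 6.3.6, asked before Dose 4.
- Start Group 2's second AE collection period at Visit 8. Align the Protocol Summary, the Group 2 Schedule of Activities, section 3, footnote a in 8.1, and 8.1.4.
- In the SAP, report Group 2 AEs from Visit 8 to Dose 4 as a separate row, ending at Visit 9 or withdrawal if Dose 4 is not given. The denominator should be all Group 2 infants in the overall safety population who received Prevnar 13 at Visit 8. The Dose 4 safety population (SAP 4.1) would not do, because it requires receipt of Dose 4 and so drops an infant withdrawn after a reaction at Visit 8.
- Leave the endpoint counted from Dose 4 as it is.

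The cost is somewhat more nonserious AE recording and coding, a changed CRF date window, and one more table row. No visit, procedure or blood draw is added. Prompted reactions after the 12-month Prevnar 13 dose would remain uncollected, and the new row should carry a note saying so.
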